3.3 Intervention

Experimental intervention: At the posterior sacroiliac joint ligament just inferior to the posterior superior iliac spine, 40mg of methylprednisolone acetate (1cc) combined with 1cc of 1% Lidocaine will be injected using a 1.5 inch 25 gauge needle. The medication will be injected unilaterally if pain is single sided or bilaterally for a total of 4cc of medication if the pain is in both

sacroiliac joint regions. The subject will subsequently receive once weekly physical therapy for 4 weeks.

Control intervention: At the posterior sacroiliac joint ligament just inferior to the posterior superior iliac spine, 2cc of saline with 1cc of 1% Lidocaine will be injected using a 1.5 inch 25 gauge needle. The medication will be injected unilaterally if pain is single sided or bilaterally for a total of 4cc of placebo saline if the pain is in both sacroiliac joint regions.

The subject will subsequently receive once weekly physical therapy for 4 weeks

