1.2 Specific study objectives

Primary question and response variable:

Does ultrasound guided posterior sacroiliac ligament corticosteroid injection combined with lidocaine provide superior pain relief in pregnant women with PGP in the second or third trimester compared with a saline with lidocaine active comparator injection as measured by the pain Numeric Rating Scale (NRS) (0-10)?

Primary outcome variables: Pain NRS (0-10) (anchors: 0 = none, 10 = worst imaginable)

Secondary questions and response variable:

Does posterior sacroiliac ligament corticosteroid injection combined with lidocaine in pregnant women with PGP in the second/third trimester result in less disability and improved physical examination as compared with a saline with lidocaine active comparator injection?

Secondary outcome variables: Oswestry Disability Index (ODI), Pelvic Girdle Questionnaire (PGQ) and physical examination testing including the Patrick's Faber test, the Posterior Pelvic Pain Provocation test (PPPP or P4), long dorsal ligament (LDL) palpation, pubic symphysis palpation, the modified Trendelenburg test and the Active Straight leg raise (ASLR) test.

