Those randomized to the will receive either 40mg of a non-fluorinated injectable glucocorticoid, methylprednisolone acetate (1cc) combined with 1cc of 1% Lidocaine or 1cc f1% Lidocaine plus 1cc of normal saline. The injection will be performed unilaterally if pain is single sided or bilaterally if the pain is in both sacroiliac joint regions The injection will be ultrasound guided and performed by the PI [name] who is trained in musculoskeletal ultrasound and ligamentous injections as a specialist in physical medicine and rehabilitation. [name] and the participant will both be blinded to the type of injectate used. Study visits 2 and 3 will include the same questionnaires and physical examination and will document any change in the pregnancy status. Study visit 4 will occur 6 weeks post-delivery and will include the same questionnaires and physical examination to determine if any chronic pain remains. Patients will be allowed to utilize acetaminophen as needed and the amount utilized in each intervention arm will be recorded. Total study visit time is expected to be 60 minutes for study visit 1 and 30 minutes for visits 2-4. Standard physical examination maneuvers validated for the assessment Protocol Version 4 – 03-06-2015

of pregnancy related PGP will be performed by the PI [name] and include pelvic pain provocation tests and functional stability testing. It will be noted with each maneuver whether the test was positive or negative. They will include:

a. *Patrick's Faber test*: With the patient in supine, the patient's leg is flexed, abducted and externally rotated so that the heel rests on the opposite kneecap. This test is positive with production of pain in the sacroiliac joint.

b. *Posterior Pelvic Pain Provocation (P4) test*: with the patient supine, the femur is flexed to be perpendicular with the table at 90 degrees and the knee is flexed at 90 degrees. A gentle force is applied to the femur in the direction of the examination table. The test is positive when the patient experiences pain in the gluteal region of that leg.

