3.5.4 Follow-up

Patients will be instructed to contact the study nurse coordinator blinded to the study hypotheses with any side effects: flushing, nausea, vomiting, insomnia, and/or worsening pain at any time during the first week. The study nurse coordinator will then contact each patient by phone on day 7 after the injection regarding medication tolerance. After the four weeks of physical therapy, patients will return for a repeat questionnaire administration and physical examination. Questionnaires will be performed prior to physical examination so as not to

Protocol Version 4 – 03-06-2015

influence pain scores. During the course of physical therapy, they will be reminded by the physical therapist to follow-up with study visit 2 and reminder letters mailed the week prior to study visit 2. Study visit 3 will be performed eight weeks post injection to determine if the intervention has a lasting effect. Study visit 4 will occur 6 weeks post-delivery and will include the same questionnaires and physical examination to determine if any chronic pain remains.

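### The control injection has two conflicting recipes (2 cc per side in section 3, 3 cc per side in section 3.3); following section 3.3 would unbalance the arms and could unblind the injecting PI

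*Combined protocol and SAP*

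**What the plan says.** Three places in the Combined protocol and SAP fix what is injected.

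- **Active arm (section 3 narrative and section 3.3).** Both give 40 mg methylprednisolone acetate in 1 cc, mixed with 1 cc of 1% lidocaine, per side. Section 3.3 adds that patients with pain on both sides are injected "bilaterally for a total of 4cc of medication if the pain is in both" sacroiliac regions.
- **Control arm, section 3 narrative (before section 3.1).** One cc of 1% "Lidocaine plus 1cc of normal saline".
- **Control arm, section 3.3.** "2cc of saline with 1cc of 1% Lidocaine will be injected using a 1.5 inch 25 gauge needle". For pain on both sides it is given "bilaterally for a total of 4cc of placebo saline if the pain is in both sacroiliac joint regions".

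On blinding, the section 3 narrative says that the PI "and the participant will both be blinded to the type of injectate used". The same PI gives the injection. The standard examination manoeuvres for the assessment "of pregnancy related PGP will be performed by the PI", and section 3.4 also assigns the examination procedures to the PI. Section 1.2 lists those tests (P4, long dorsal ligament palpation, ASLR and others) as secondary outcomes. The primary outcome is the patient's own 0-10 pain rating.

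The only concealment device described is the set of identical precoded envelopes in section 3.5.2. The documents do not say who draws up the syringes, whether they are masked, or that volumes are matched.

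**The concern.** The research question is whether corticosteroid adds anything to a lidocaine injection. A clean answer needs a comparator that differs from the active injection only in the corticosteroid. The section 3 recipe meets that in volume and lidocaine concentration. The section 3.3 recipe does not. Section 3.3 is also the dedicated Intervention section, so it is where someone preparing a syringe would naturally look.

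Three things are at stake.

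1. **The comparator is not uniquely defined.** Staff cannot follow both recipes, and every control injection would depart from one section or the other. If different staff used different sections, the control arm would be a mixture.
2. **The treatment contrast.** Under section 3.3 the arms would also differ in injected volume and lidocaine dilution.
3. **The PI's blind.** The PI knows whether an injection is unilateral or bilateral. Given that, an unmasked 3 cc fill against a 2 cc fill per side would identify the arm in every patient. The injection is at visit 1, before every follow-up examination, so any unblinding would carry through all of them. The safety monitoring plan also has the PI and/or study physician judge how adverse events relate to study drug, and that judgement would be exposed too.

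**Working it through.** **Inputs.** Active recipe: section 3 narrative and section 3.3, which agree. Control recipe A: section 3 narrative. Control recipe B: section 3.3. A 1% solution contains 10 mg per cc.

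**Formulas.** Volume per side = sum of the components. Bilateral volume = 2 × volume per side. Lidocaine dose = cc of 1% lidocaine × 10 mg/cc. Lidocaine concentration = 1% × (cc lidocaine ÷ total cc).

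**The plan's own bilateral totals first.**

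- Active: 2 × (1 + 1) = 4 cc. This reproduces the stated 4 cc, so in the active arm the figure counts whole injectate.
- Control, recipe B, saline only: 2 × 2 = 4 cc. This reproduces the stated 4 cc.
- Control, recipe B, whole injectate: 2 × (2 + 1) = 6 cc. This does not.
- Control, recipe A, whole injectate: 2 × (1 + 1) = 4 cc. This reproduces it.
- Control, recipe A, saline only: 2 × 1 = 2 cc. This does not.

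The control total of 4 cc therefore fits recipe B if it counts saline alone, and recipe A if it counts whole injectate as in the active arm. It does not decide between them.

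**The arms side by side.**

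| | Active | Control A (section 3) | Control B (section 3.3) |
|---|---|---|---|
| Volume per side | 1 + 1 = 2 cc | 1 + 1 = 2 cc | 2 + 1 = 3 cc |
| Bilateral volume | 4 cc | 4 cc | 6 cc |
| Volume relative to active | – | 2/2 = 1.0 | 3/2 = 1.5 |
| Lidocaine dose per side | 10 mg | 10 mg | 10 mg |
| Lidocaine dose, bilateral | 20 mg | 20 mg | 20 mg |
| Lidocaine concentration | 1% × 1/2 = 0.50% | 1% × 1/2 = 0.50% | 1% × 1/3 = 0.33% |

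Recipe A matches the active arm on every row. Recipe B matches it only on lidocaine dose.

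**Could the conflict come from the PDF reading?** The section 3 sentence has a garbled character and a missing word, but its volumes are legible. The section 3.3 sentence is complete. Neither is amendment-log text, so the conflict is in the plan itself.

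**The case against.** The strongest reply is that section 3.3 is probably a slip. It gives the same 4 cc bilateral total for both arms in parallel sentences, and in the active arm that total is whole injectate. Section 4 uses the word placebo for the comparator as a whole, so the control total can naturally be read as 4 cc of whole injectate, or 2 cc per side as in section 3. That reading is plausible and may well be what was intended. But the saline-only reading fits section 3.3 exactly as printed, and nothing says which section governs. A slip in the operative recipe still has to be corrected before anyone follows it.

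Second, the blinding harm needs two conditions that the documents do not establish: that recipe B is used, and that the PI can see the fill. This stands, and the blinding point is conditional for that reason. The contradiction itself is not.

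Third, the reach is limited. The lidocaine dose is equal under either recipe. The primary pain score is patient-rated, and section 3.5.4 puts it ahead of the examination ("Questionnaires will be performed prior to physical examination so as not to" affect the pain ratings). Nothing shows that participants would be unblinded, and the documents give no basis for putting a number on any bias from 1 cc of extra saline. All of this stands. It confines the blinding risk mainly to examiner-scored secondary outcomes and to the PI's other judgements.

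Fourth, silence on syringe preparation and masking is a separate omission, which would remain even with equal volumes. That is right. The recipe correction is justified without it, and masking belongs in the same paragraph only because the PI both injects and examines.

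**Conclusion.** The concern holds, and section 3.3 is wrong as written. The control injection has two incompatible operative recipes, 2 cc and 3 cc per side, and the text does not resolve them.

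If section 3.3 is followed, control volume is 1.5 times active volume (3 v 2 cc per side, 6 v 4 cc bilaterally) and lidocaine concentration is 0.33% against 0.50%, at an equal lidocaine dose. Unless syringes are masked, the volume could then reveal the arm to a PI who is declared blinded and performs the secondary examination tests. If the section 3 recipe is followed, none of these differences arises.

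The documents do not show which recipe was used, so no bias in any outcome is claimed or estimated. The point must be fixed because the comparator is half of the treatment contrast and is not uniquely defined.

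**What to change.** Correct the control paragraph of section 3.3 to the volume-matched recipe in section 3: 1 cc of saline plus 1 cc of 1% lidocaine, 2 cc per side. State the bilateral total as 4 cc of whole injectate in both arms, replacing the present saline total for control. Both arms then receive 2 cc per side with lidocaine at 0.50%, and differ only in whether the other 1 cc is methylprednisolone acetate or saline.

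In the same paragraph, state that someone other than the PI prepares the syringes and that they are masked.

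The cost is one corrected paragraph and a matching preparation instruction. Patient numbers and visits do not change.

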3.4 Consent process

Patients will be identified when they arrive for a scheduled MD appointment at any point during their second or third trimester. They will be given a flyer with information about the study and will be asked to participate. A separate study visit 1 time will then be scheduled. At study visit 1, if the patients meet eligibility criteria, a consent form will be read to them describing the nature of the trial and potential associated risks and benefits. They will be informed that neither participation nor refusal will influence the care received at either Loyola University Medical Center or Gottlieb Hospital. They will be asked a few questions afterwards to verify comprehension and then sign the consent form documenting their agreement to participate. A copy of the consent form will be given to them. Participation is completely voluntary and they may discontinue participation in the study at any time. Patients will complete the informed consent process at study visit 1. A study coordinator ([name]) or the PI ([name]) will consent all patients. The patients who consent to participate will be given a set of questionnaires at that time and asked to complete them during study visit 1. Consenting patients will undergo systematic examination procedures. These procedures will be performed by the PI. Patients will receive parking vouchers for each study visit.

3.5 Trial design

Randomized double blinded controlled clinical trial

3.5.1 Pre-Enrollment

Protocol Version 4 – 03-06-2015

Eligible participants will be informed about this trial during any second or third trimester visit when they complain or present clinically with PGP in the office. Special efforts will be made to increase enrollment in certain subgroups (minorities). No other medical or other documentation will be required for determining eligibility. After assuring eligibility, patients may proceed to study visit 1 where consent and randomization will take place. With prevalence rates of PGP in pregnancy at 45%, there will be ample availability of eligible participants. Sixty total participants will be enrolled.

3.5.2 Randomization

Randomization strategy will be developed in collaboration with Loyola Biostatistics Department, using blocks of 3 stratified on pain location and allocation will be a 1:1 ratio of patients in the intervention and control groups. The randomization procedure will take place at study visit 1 after informed consent is completed and eligibility status is determined. A research coordinator ([name]) blinded to the study will give precoded identical envelopes with randomization assignments to the patients at the conclusion of study visit 1. This assistant and an independent Data and Safety Monitoring Board (DSMB) will have access to the randomization code.

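### Section 3.5.2 pairs blocks of 3 with 1:1 allocation but gives no rule that reconciles them; secondarily, the coordinator described as blinded appears to hold the randomization code

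*Combined protocol and SAP*

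**What the plan says.** Section 3.5.2 (Randomization) leaves the strategy to be worked out jointly with the Loyola Biostatistics Department. It describes the method as "using blocks of 3 stratified on pain location and allocation will be a 1:1 ratio of patients in the intervention and control groups". The number of strata is not given. No other section gives another block size or a rule for combining blocks that favour different arms. Section 3.5.1 sets enrolment at 60, and the sample-size appendix assumes equal groups: 25 per arm, raised to 30.

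On timing, section 3.5.2 says: "The randomization procedure will take place at study visit 1 after informed consent is completed and eligibility status is determined". A research coordinator "blinded to the study will give precoded identical envelopes with randomization assignments to the patients at the conclusion of study visit 1". The next sentence reads: "This assistant and an independent Data and Safety Monitoring Board (DSMB) will have access to the randomization code".

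Other places bear on who is blind and who meets patients:

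- Section 3 (Protocol) says of the PI, who injects, that the PI "and the participant will both be blinded to the type of injectate used".
- Section 3.4 (Consent process) says: "A study coordinator ([name]) or the PI ([name]) will consent all patients". Of the examinations it says: "These procedures will be performed by the PI".
- Section 3.5.4 (Follow-up) tells patients to "contact the study nurse coordinator blinded to the study hypotheses with any side effects".
- Sections 3 and 3.5.3 place the injection at study visit 1.

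**The concern.** **Block size.** Three patients cannot be divided equally between two arms, so block size and ratio pull against each other within one sentence. A statistician given this text has to choose between repeating one split, randomizing the direction of each block, or forcing equal numbers of 2:1 and 1:2 blocks. The three choices produce different trials, and a later reader could not tell from the plan which was used.

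**Code access.** The only person in section 3.5.2 to whom the words about the assistant can naturally refer is the coordinator just described as blinded. Someone with access to the code is not blind to allocation. If the code is the list of upcoming assignments and its holder also consents patients, allocation concealment is at risk. If the holder administers questionnaires, someone who can find out the arm is present when the patient-reported primary outcome is collected.

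**Working it through.** **Inputs.** Block size 3 and ratio 1:1 (section 3.5.2); 60 enrolled (3.5.1); two-sided alpha 0.05 and 80% power (3.7); difference of 2 NRS points and SD 25 mm, read here as 2.5 NRS points (sample-size appendix). The standardized difference is 2/2.5 = 0.8.

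**The plan's own figure.** The appendix formula, Δ/σ = 3.96/√n, gives n = (3.96 × 2.5/2)² = 24.50, so 25 per group. The usual normal formula gives 24.53, also 25. The stated 50 in total reproduces, with equal arms.

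**Block arithmetic.** The smallest imbalance in a complete block of size b is the minimum of |2k − b| over k = 0,…,b. It is 1 for b = 3 and 0 for b = 2, 4 or 6.

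**Three ways to build a list of 60** (20 full blocks of 3; this is an assumption, since strata may leave blocks unfilled):

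| Rule, none of them stated | Arms | t-test power, all 60 analysed |
|---|---|---|
| Ten 2:1 and ten 1:2 blocks | exactly 30:30 | 86.1% |
| Direction random, probability 0.5 each | varies | 86.0% on average |
| Same 2:1 split every time | 40:20 | 81.9% |

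For the random rule, let X be the number of blocks favouring one arm, X ~ Binomial(20, 0.5). The arms are 20 + X and 40 − X, so they differ by |2X − 20|. Then P(exactly 30:30) = 17.6%, P(difference ≥ 6) = P(|X − 10| ≥ 3) = 26.3%, and P(difference ≥ 10) = P(|X − 10| ≥ 5) = 4.1%.

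For the repeated split with only 50 analysed (33:17), the normal approximation gives 76.4%, against 80.7% at 25:25.

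**Even blocks.** In simulated lists of varied 4/6 blocks, the difference within a stratum never exceeded 3. With two strata of 30 (an assumption) the total difference never exceeded 4, and at 32:28 power is 86.0%.

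**Predictability**, for someone who knows the possible block sizes and all past assignments:

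- Mixed blocks of 3: six equally likely sequences. The third place is forced in 2 of 6, so (2/6)/3 = 11.1% of assignments are certain. Best-guess accuracy is (1/2 + 2/3 + 2/3)/3 = 61.1%.
- Fixed blocks of 4: the last place is always forced and the third is forced with probability 1/3, so (1/3 + 1)/4 = 33.3% are certain. Best-guess accuracy is (1/2 + 2/3 + 2/3 + 1)/4 = 70.8%.
- Varied 4/6 (simulated, sizes equally likely): 5.5% certain, 69.1% best guess.

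Even blocks are therefore not harder to guess on every measure.

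**Code access.** No arithmetic applies. Read together, the two sentences of 3.5.2 give one person two descriptions: blinded to the study, and holding access to the code. The wording in 3.5.4 suggests that the first may mean blind to the hypotheses. That would remove the verbal clash but would not make the person blind to allocation. The effect of this on NRS scores cannot be computed from the documents.

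**The case against.** The ratio can be read as a property of the whole list rather than of each block. A reader might infer that blocks of 3 make 1:1 impossible, or possible only in expectation. The documents do not support that, because a balanced mix gives exactly 30:30. With random direction the power cost is negligible, and the details were still to be worked out with the Biostatistics Department. All of this stands. What remains is that the mixing rule is absent and that the wording does not exclude the costly 40:20 version.

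On code access, a reader might infer that the plan flatly contradicts itself, or that concealment and blinding are broken. That goes too far:

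- Blinded to the study may mean blinded to the hypotheses, as 3.5.4 says of the study nurse coordinator.
- The persons stated to be blind to the injectate are the PI and the participant, and 3.5.2 does not contradict that.
- The PI does the examinations, and the blinded patient completes the NRS herself.
- Randomization follows consent and eligibility.
- Names were removed, so it cannot be told whether the research coordinator of 3.5.2 is the study coordinator who may take consent under 3.4.
- The code may be the upcoming list or only a key from envelope codes to arms.

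These points lower the confidence to moderate. They do not answer the remaining gap: section 3.5.2 does not say what access to the code entails for a person it calls blinded, or which duties that person may hold.

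Nor should a reader infer that the envelopes reveal treatment. They are precoded and identical, so a code is the natural reading.

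**Conclusion.** The main point holds with high confidence. Block size and ratio do not fit together as written, and the plan supplies no rule to join them. It should be corrected, although it is not in itself a power problem. The loss is about 0.1 percentage point if block direction is random, and reaches about 4 points (86.1% to 81.9%) only if one 2:1 split is repeated. These figures assume SD 2.5, a 2-point difference, 20 full blocks and all 60 analysed.

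The secondary point holds with moderate confidence: whoever has the code is not blind to allocation, whatever the adjective was meant to convey. Whether concealment is harmed depends on facts that the documents do not give.

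One item is for clarification only. Envelopes are handed out when study visit 1 ends, yet the injection is given during that visit, so the order of events needs stating.

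**What to change.** In section 3.5.2:

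1. Replace blocks of 3 with permuted blocks of even size (for example 4, or 4 and 6 varied at random) within the pain-location strata. Do not disclose the sizes to the site; this matters most if one fixed size is used.
2. Have the Biostatistics Department, already named there, generate and hold the list.
3. Say what the randomization code is. Drop or define the description of blinding for anyone with access to it.
4. State that whoever holds the code does not consent patients or administer questionnaires.
5. Reconcile the envelope step with the injection at the same visit.

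The cost is a few sentences and a new list, with no extra patients. The separation in item 4 is meant to be met by dividing duties among existing staff, not by adding a dedicated person. Section 5 puts the start of recruitment in 2014 and this version is dated 03-06-2015, so enrolment may have begun. In that case the new list is an amendment that applies only to assignments not yet made, and the plan should record the block rule used until then.

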Patients will be approached in their second or third trimester regarding the study in the Obstetrics or Rehabilitation clinics if they have PGP. They will be given a flyer regarding the study. If interested in participating, they will either proceed to study visit 1 (baseline), if time permits, or set up a separate time for study visit 1 to take place. Patients will be consented and evaluated for eligibility at this baseline visit. Eligible patient will be randomized to either the control or intervention groups at study visit 1. They will receive the injected medication at study visit 1. This study will require study visits total, study visit 1 will be at the time of randomization,

study visit 2 will be 4 weeks after injection, study Visit 3 will be at 8 weeks after start of intervention/after injection. and study visit 4 will be 6 weeks post-delivery. There will be one follow-up phone call between visit 1 and 2 on day 7 following intervention to inquire about any medication side effects or adverse events. Study duration is 8 weeks per patient, with an expected two year total recruitment and data collection time period. At study visit 1, patients will be randomized to receive the intervention medication or active comparator and undergo a physical examination of the external musculoskeletal pelvis and will complete the NRS for 'worst pain' and 'mean pain' during the latest 48 hours, a pain diagram, a personal health information questionnaire regarding their pregnancy, past medical history, activity level and restrictions. Disability as measured by the Pelvic Girdle Questionnaire (PGQ) and Oswestry Disability Index (ODI), Health-Related Quality of Life (HRQL) measured by the Wellbeing NRS and work ability will be measured with one question from Workability Index i.e. "Current work ability compared with the lifetime best".

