3.5.3 Intervention administration

The injection intervention will be administered at study visit 1 following successful recruitment and consent. Since physical therapy is considered standard of care treatment in the management of pregnancy related PGP, all participants will need to have failed PT.

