Appendix II: Sample Size Calculations

Sample size was determined under the assumption that a difference of 2 on NRS would have clinical relevance. This was based on the previous work of Elden¹⁴ in an RCT for acupuncture compared with sham for PGP in pregnancy. The 2 point difference on the NRS has also been used in other gynecologic RCTs in the measurement of pain.³³ The standard deviation of 25 mm was derived from the prior work of Bastiaenen¹⁶ in an RCT comparing a specific educational physical therapy program to usual care in postpartum PGP. No standard deviations were available in the Elden paper or in any other literature on this topic. For the primary outcome of patient pain ratings (0-10 NRS) after 4 weeks of physical therapy with or without methylprednisolone, a sample size of 50 (25 in each group) will give the study 80% power to identify a 2 point difference on the NRS (with [alpha] of .05). The 4 week follow-up time period is used because the clinical effect of the study medication is expected within the 4 weeks. An additional 5 participants in each group is added to account for a loss to follow-up of 10% which calculates to then 30 per treatment group. Power analyses were performed by using STATA

11.0. The basic formula for calculation is $\Delta/\sigma = 3.96/\sqrt{n}$, with Δ = effect size, σ = the standard deviation and n = number of patients needed.

Sensitivity analysis

Expected change in NRS (Effect size)	N if Power 80%	N if Power 90%
1	198 (99 per group)	264 (132 per group)
1.5	88 (44 per group)	118 (59 per group)
2	50 (25 per group)	66 (33 per group)
3	22 (11 per group)	30 (15 per group)

References:

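### The randomization section hands patients envelopes holding their assignments, which contradicts the stated participant blinding and leaves no route from the assignment to the syringe

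*Combined protocol and SAP*

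**What the plan says.** Section 3.5.2 gives the only rule for delivering the allocation. On timing it says: "The randomization procedure will take place at study visit 1 after informed consent is completed and eligibility status is determined". A research coordinator, described as blinded, then "will give precoded identical envelopes with randomization assignments to the patients at the conclusion of study visit 1". The section closes with: "This assistant and an independent Data and Safety Monitoring Board (DSMB) will have access to the randomization code".

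On blinding, the Section 3 narrative says of the injecting investigator (the PI) that she "and the participant will both be blinded to the type of injectate used". Sections 1.3 and 3.5 call the trial double blinded.

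On the injection, the Section 3 narrative says "They will receive the injected medication at study visit 1", and Section 3.5.3 says "The injection intervention will be administered at study visit 1 following successful recruitment and consent".

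On the outcome, Section 1.2 gives "Primary outcome variables: Pain NRS (0-10) (anchors: 0 = none, 10 = worst imaginable", and Appendix II makes clear that the patient is the rater: "For the primary outcome of patient pain ratings (0-10 NRS) after 4 weeks of physical therapy".

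**The concern.** The envelope carries the assignment, and the stated recipient is the one person who rates the primary outcome and is meant not to know her arm. The stated time also fits poorly. An assignment has to reach whoever fills the syringe before the injection, yet the hand-over is put at the end of the visit in which the injection is given. The protocol does not say who opens an envelope, who prepares the syringe, or how its contents are kept from the patient and the PI.

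The stake is every efficacy outcome. The NRS, ODI and PGQ are self-reported. The six examination tests in Section 3 are scored by the PI, but each depends on what the woman reports: pain for the Faber, P4, long dorsal ligament, symphysis and modified Trendelenburg tests, and heaviness, difficulty or ease for the ASLR. If patients learned their arm, none of these would be protected, and the analysis could not undo it.

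**Working it through.** **Comparing the sections**

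| Question | What the protocol says | Where |
|---|---|---|
| Who receives the envelope? | The patient | 3.5.2 |
| What does it hold? | A randomization assignment, in a precoded envelope | 3.5.2 |
| When is it handed over? | Conclusion of visit 1 | 3.5.2 |
| When is randomization done? | Visit 1, after consent and eligibility | 3.5.2 |
| When is the injection given? | Visit 1, after consent | 3 (narrative), 3.5.3 |
| Who is blinded? | Participant and injecting PI | 3 (narrative) |
| Who may see the code? | The coordinator and the DSMB | 3.5.2 |
| Who prepares the syringe? | Not stated | – |
| What is the order of steps within visit 1? | Not stated; Appendix I only marks that each is done at visit 1 | – |

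Rows 1, 2 and 6 conflict unless the envelope shows only a masked code, which no section says. Rows 3 and 5 fit together only if the injection is the very last act of the visit. Even then, nothing links the patient's envelope to the person filling the syringe. Separately, a coordinator with access to the code is not blinded in the usual sense, although Section 3.5.2 uses that word.

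**The plan's own figure**

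Appendix II gives SD 25 mm (2.5 NRS points), a 2-point difference, two-sided alpha 0.05 and 80% power. Its formula, Δ/σ = 3.96/√n, gives n = (3.96 × 2.5 / 2)² = 24.5, rounded up to 25 per group. This matches the stated 25. The present point does not depend on it; it only supplies the SD and n used below.

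**What a reporting shift would do**

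Suppose there is no true effect, but knowledge of the arm moves the mean reported NRS by d points between arms. Using a two-sample t-test:

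- Standard error = 2.5 × √(2/25) = 0.707; degrees of freedom = 48; critical value = 2.011.
- Noncentrality = d / 0.707.
- False-positive rate = P(|T| > 2.011), with T noncentral t.

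| Assumed shift d | Noncentrality | Two-sided error rate, 25 per group |
|---|---|---|
| 0 (arm not learned, or no effect on reporting) | 0 | 5.0% |
| 0.25 | 0.354 | 6.4% |
| 0.5 | 0.707 | 10.7% |
| 1.0 | 1.414 | 28.3% |

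If all 30 enrolled per group were analysed, the standard error would be 2.5 × √(2/30) = 0.645, and the 0.5 and 1.0 rows would become 11.9% and 33.2%.

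The shifts are assumptions; the documents give no figure for them. Each is an average over the whole arm, so it needs enough patients to know their allocation to move the group mean. The t-test stands in for the planned test: Section 3.8 names Mann-Whitney if the data are not normal.

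**The case against.** The strongest reply is that the envelope probably shows a code. The envelopes are precoded and identical, and the next sentence limits access to the randomization code to the coordinator and the DSMB. That restriction makes most sense if the patient sees only a masked label. No section says that she opens the envelope or that it names the drug. On this reading she learns nothing and the error rate stays at 5%. This stands as a plausible reading, so a reader who infers from Section 3.5.2 that patients will be unblinded goes further than the documents do.

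A second reply concerns timing. A reader might infer that the injection has already been given when the envelope appears, so that the envelope cannot direct it. The documents do not establish this. The order of steps within visit 1 is never listed, and the injection could be the last act, after consent, questionnaires and examination. This also stands: the timing is a poor fit, not a proven impossibility.

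A third reply is that Section 3.5.2 leaves the randomization strategy to be developed with the biostatistics department, so operational detail may follow. That would explain missing detail. It does not explain a sentence that names the recipient and the moment, and names a recipient who is supposed to be blinded. Staff who follow that sentence literally would put the assignment in the outcome rater's hands. If the envelope holds only a code, giving it to the patient serves no stated purpose, and the route to the syringe is still absent.

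**Conclusion.** The point holds as an internal contradiction: the stated participant blinding is contradicted by the stated envelope rule, and the protocol gives no route from the assignment to a masked syringe. This is wrong as written and goes beyond thin detail, because following the sentence creates a risk of bias in a trial whose primary outcome the patient rates herself.

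The size is conditional. If patients do not learn their arm, there is no inflation from this source. If they do, the false-positive rate is about 11% for an average between-arm shift of 0.5 point and about 28% for 1.0 point, assuming SD 2.5, 25 per group, no true effect and a t-test. Both shifts are well below the 2-point target difference. These figures illustrate the exposure; they do not predict the trial's error rate.

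**What to change.** Replace the envelope sentence in Section 3.5.2 with wording to this effect: *After consent, confirmation of eligibility and all baseline assessments, and before the injection, the next sealed envelope is opened only by the site pharmacy or by a designated staff member who has no part in consent, enrolment, questionnaires, examinations or the day-7 call. That person prepares the syringe out of sight of the patient and the PI, covers it, and labels it with the study number only. The envelope is never given to the patient or the PI.*

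The separation of roles matters. Section 3.5.2 gives the code to a coordinator it calls blinded, and Section 3.4 has a study coordinator or the PI consenting all patients. Names are removed, so these may or may not be the same person. Passing syringe preparation to a code-holder who also enrols patients would trade a blinding problem for an allocation-concealment problem. Section 3.5.2 should therefore either remove that coordinator's access to the code or stop describing the role as blinded and keep it away from consent, enrolment and assessment.

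The cost is a wording change and an opaque cover and label for each syringe. If the pharmacy is not used, one existing staff member is also kept out of recruitment and assessment roles. No dose, visit, sample size or analysis changes.
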